4.4. Eligibility Criteria

4.4.1. Inclusion Criteria

Sites which:

Imperial Clinical Trials Unit	ZODIAC STATISTICAL ANALYSIS PLAN – MAIN ANALYSIS	V1 17 th Jan 2024
-------------------------------	--	------------------------------

- Manage ACS patients as defined by: Symptoms of myocardial ischemia with an unstable pattern, occurring at rest or with minimal exertion, within 72 hours of an unscheduled hospital admission due to presumed or proven obstructive coronary disease and at least one of the following:
 - Elevated cardiac biomarkers
 - Resting electrocardiographic changes consistent with ischemia or infarction, plus additional evidence of obstructive coronary disease from regional wall motion or perfusion abnormality, 70% or more epicardial coronary stenosis by angiography, or need for coronary revascularization procedure
- Manage post ACS follow up care of patients including risk factor control
- Can provide follow up information on patient care for a maximum of 16 weeks including blood tests
- Are willing/ able to access and undertake training for the DSS
- Have adequate internet connection at site and the ability to access the DSS
- Have no restrictions on use of LLT (within national guidelines/ reimbursement)
- Collect patient information essential for DSS input on all of the following:
 - LDL-C, TC, HDL-C measurements.
 - Record of corresponding lipid-lowering therapy at the time the LDL-C is measured.
 - Estimated glomerular filtration rate (eGFR), e.g. available or derived using Modification of Diet in Renal Disease (MDRD)², or its component, the serum creatinine.
 - Patient's demographics (age, gender), clinical history (ASCVD, coronary artery disease, cerebrovascular disease, abdominal aortic aneurysm, peripheral artery disease, diabetes melitus), systolic blood pressure, smoking status.

Patients who:

- Are aged ≥ 18 to < 80 years old
- Can provide written informed consent
- Present to a study site with ACS as LLT naïve, monotherapy or combination therapy (defined as more than one LLT agent)
- Are willing to take LLT for the secondary prevention of CV disease

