4.5. Sample Size

It is estimated that in the SoC arm, we expect 7% of patients to be on combined therapy at 24 weeks. This estimate is based on published data (Koskinas et al³) using the ELIPS study cohort which included exclusively ACS patients. A slightly lower proportion of patients (5%) may be expected to be on combination therapy at 16 weeks.

To detect a meaningful difference in proportions from the SoC group of 0.05 to 0.15 in the DSS with 90% power, we require 744 patients in 24 clusters within each arm.

This calculation assumes a two-sided statistical test at the 5% significance level, ICC of 0.1 and clusters of a similar size (31 for each site).

Justification for ICC of 0.1: Based on the article by Campbell et al.⁴, it would be reasonable for a guideline implementation study within primary care to assume an ICC of the order of 0.1 for process variables and an ICC of less than 0.05 for the outcome variable. This is also in line with empirical estimates obtained from an online database with ICC reported for cluster studies that aimed to change practice.⁵ In the database we examined the hypertension guideline interventions, these varied from 0.048 to 0.064. In addition, we have to consider clustering within country; to be conservative we have assumed an ICC of 0.1.

Based on our experience working in this setting we do not expect any loss of clusters. However, drop out may occur within clusters. As data are extracted from routinely collected electronic healthcare records, we expect missing data to be low as it will only be patients who actively request data collection to stop that will have missing outcome data. Considering a conservative approach⁶ and assuming a loss to follow-up rate of 5%, we need a minimum total sample size of 1568. Considering adjusted numbers per cluster we aim to recruit 792 over 24 clusters per arm (a total sample size of 1584).

Imperial Clinical Trials Unit	ZODIAC STATISTICAL ANALYSIS PLAN – MAIN ANALYSIS	V1 17 th Jan 2024
----------------------------------	--	------------------------------

All calculations were done using PASS 2022 software⁷ and applying a method of “Tests for Two Proportions in a Cluster-Randomised Design”.

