age, sex, and comorbidities (diabetes, time since first CV diagnosis) and at site level, type of site and country in the imputation model. We do not anticipate cluster-level variables to be missing. The appropriateness of the assumption of approximate normality of the random effect of this model will be assessed graphically.

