8.8. Subgroup Analysis (of Primary Outcome)

Subgroup analysis will follow the same analysis of the primary outcome with the addition of an interaction term between the treatment and the subgroup analysis variables. These will be summarised by forest plots.

The variables investigated in the subgroup analyses are (at patient level):

- gender (men vs women)
- age (below vs above or equal to median age)
- diabetes (yes vs no)
- LLT naïve (yes vs no)
- patients experiencing one or more CV event in the 2 years prior to admission

Below is an example model for an interaction between intervention and gender added.

$$\log(\pi_{ij}) = \beta_0 + \beta_1 ACSDSS_{ij} + \beta_2 COUNTRY1_{ij} + \beta_3 COUNTRY2_{ij} + \beta_4 Site\ type_{ij} + \beta_5 Site\ type_{ij} + \beta_6 Gender_{ij} + \beta_7 ACSDSS_{ij} * Gender + U_j$$

Where:

- π_{ij} : probability of combination therapy for the i^{th} patient in j^{th} site
- $ACSDSS_{ij}$: dummy variable for intervention ($ACSDSS_{ij} = 0$ or 1) for patient i in j^{th} site
- $COUNTRY1_{ij}, COUNTRY2_{ij}$: dummy variable for COUNTRY ($COUNTRY_{ij} = 0$ or 1) for patient i in j^{th} site
- $Site\ type1_{ij}, Site\ type2_{ij}$: dummy variable for Site Type ($Site\ type_{ij} = 0$ or 1) for patient i in j^{th} site type
- U_j : random effect for site $j \sim N(0, \sigma_u^2)$
- $Gender_{ij}$: dummy variable for gender of patient i in j^{th} site

Subgroup analyses at cluster level by site type is not planned as the number of sites is anticipated to be small for some strata.

Imperial Clinical Trials Unit	ZODIAC STATISTICAL ANALYSIS PLAN – MAIN ANALYSIS	V1 17 th Jan 2024
-------------------------------	--	------------------------------

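### Section 8.8 tests the age interaction only through a median split, which keeps about 64–75% of the information in continuous age if the effect changes linearly with age

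*SAP*

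**What the plan says.** SAP Section 8.8 repeats the primary-outcome model "with the addition of an interaction term between the treatment and the subgroup analysis variables" and presents the results in forest plots. It lists five patient-level variables. Gender, diabetes, LLT-naïve status and a CV event in the previous two years are each used as two natural categories. Age is the only one that has to be grouped, and it is entered as "age (below vs above or equal to median age". No cut in years is given, so the median can only come from the recruited patients.

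Age is available ungrouped. Table 11 reports its mean, SD, median and range in years, and the Section 8.4 imputation model includes "age, sex, and comorbidities (diabetes, time since first CV diagnosis". The only information on its distribution is the eligibility criterion in Section 4.4.1: "Are aged ≥ 18 to < 80 years old". Neither the sensitivity analyses in Section 8.10 nor the outputs in Section 12.7 and Appendix C add an interaction with continuous age.

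**The concern.** A two-level split treats all patients on one side of the cut as the same age, and treats patients a year apart across the cut as different. If the DSS effect rises or falls steadily with age, the contrast between the two halves recovers only part of that gradient. The trial is sized for the main effect and no power is stated for any interaction, so an avoidable loss in this test makes it more likely that a real age gradient goes undetected. What is at stake is the reading of one of five supportive subgroup analyses. The primary risk ratio, its interval and its test do not depend on it.

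**Working it through.** **Inputs from the SAP.** Section 4.5: "difference in proportions from the SoC group of 0.05 to 0.15 in the DSS with 90% power"; "ICC of 0.1 and clusters of a similar size (31 for each site"; "we require 744 patients in 24 clusters within each arm"; "This calculation assumes a two-sided statistical test at the 5% significance level". Section 4.4.1: ages 18 to under 80. The documents give no age distribution and no size for an age interaction, so the shape of the age distribution and the starting power are assumed below and shown as ranges.

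**The plan's own figure.** The unpooled two-proportion formula gives (1.960 + 1.282)² × (0.05×0.95 + 0.15×0.85) / 0.10² = 183.9 per arm. The design effect is 1 + (31 − 1) × 0.1 = 4.0, so 183.9 × 4.0 = 735.5, or 23.7 clusters of 31. Rounding up to 24 gives 24 × 31 = 744 per arm. For 5% loss, 744/0.95 rounds up to 784 per arm (1,568 in total), and 31/0.95 rounds up to 33 per site, with 33 × 48 = 1,584. The sample size reproduces. It concerns the main effect only.

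**Information kept by the split.** If the log risk ratio is linear in age, the noncentrality of the split test is that of the continuous test multiplied by r, the correlation between age and the indicator of being at or above the median. Relative efficiency is r².

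- Normal ages: r = √(2/π) = 0.798, so r² = 0.637 (36% lost).
- Uniform ages: r = 0.5 / (1/√3) = 0.866, so r² = 0.75 (25% lost).
- Whole-year ages from normal distributions truncated to 18–80, mean parameter 55–70 and SD 8–15: r² = 0.637 to 0.671 (33–36% lost).

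Matching the continuous test would take 1/0.75 = 1.33 to 1/0.637 = 1.57 times as many patients.

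**Power.** Power of the split = Φ(r × (1.960 + z) − 1.960), where z is the normal quantile of the continuous test's power.

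| Continuous age | Split, normal ages | Split, uniform ages |
|---|---|---|
| 80% (z = 0.842) | Φ(0.798×2.802 − 1.960) = 61% | Φ(0.866×2.802 − 1.960) = 68% |
| 90% (z = 1.282) | Φ(0.798×3.242 − 1.960) = 73% | Φ(0.866×3.242 − 1.960) = 80% |

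The 80% and 90% are reference points, not this trial's power for an age interaction, which cannot be derived from the documents.

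**Simulation check.** Trials of 48 sites × 33 patients were simulated with risks of 5% and 15% at age 62, site effects with SD 0.6 on the log scale, truncated-normal ages (mean parameter 62, SD 10; r² = 0.658, r = 0.811) and an age gradient in the DSS arm only. The analysis was modified Poisson with site-clustered standard errors, without the stratification factors; 500 runs per slope.

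| Change in log risk ratio per 10 years | Continuous | Split | Split predicted from the continuous result and r |
|---|---|---|---|
| −0.35 | 49% | 37% | Φ(0.811×1.945 − 1.960) = 35% |
| −0.50 | 76% | 60% | Φ(0.811×2.679 − 1.960) = 58% |
| 0 | 7.6% | 5.6% | – |

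The loss is close to the formula. The last row shows rejection when there is no interaction. The Monte Carlo standard error there is √(0.05×0.95/500) = 1.0 point, so the continuous test may have been slightly anti-conservative and part of the simulated gap may reflect that. The analytic result does not depend on the simulation.

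**Stability of the cut.** In simulated trials of 1,584 patients, the whole-year median moved by about ±1 year.

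**The case against.** The best defence of the split has four parts.

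- It needs no assumption about the shape of the age effect. Nothing in the documents says that clinicians' response to the DSS should be log-linear in age, and with a true step at the median the split loses nothing. This stands. It is why the loss is stated conditionally and why the two groups should stay on display.
- It gives two balanced groups that match the four other binary subgroups in the planned forest plot. This also stands, so it would be wrong to say that the split has no benefit.
- A continuous term under a log link may add to the convergence difficulty that Section 8.4 already foresees. This is fair, but the fallback is already specified there.
- The analysis is supportive, with no sample size, decision rule or p-value threshold attached. This stands and limits the importance of the point.

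A reader might go further than the documents allow in two ways. The first is to say that the subgroup is not fixed in advance, or that a data-dependent cut biases the test. The rule is prespecified and the median uses neither arm nor outcome, so there is no room to choose a favourable cut. The second is to blame the 48 sites and the ICC of 0.1 for low interaction power. Age varies within sites, so the site effect largely cancels from the arm-by-age contrast. In 1,500 simulated trials with age independent of site and no interaction, raising the ICC from 0 to 0.1 took the SD of the main log risk ratio from 0.17 to 0.37, while the SD of the interaction stayed at about 0.17–0.18 (continuous) and 0.37–0.38 (split). The design effect of 4 belongs to the primary comparison. The sounder reason to expect limited power is that the trial is sized for the main effect.

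**Conclusion.** The point holds as a low-cost improvement of minor importance. Under a roughly linear gradient in the log risk ratio, the median split discards 25–36% of the information on age, at the upper end of that range for bell-shaped ages. At the 80% reference point this costs about 12 to 19 percentage points of power. The result rests on assumed age distributions and on approximate linearity. It does not show that the age analysis is invalid, nor that this trial would miss an age effect of any particular size.

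**What to change.** In Section 8.8, base the age interaction test on arm × age in years, with age centred and its main effect included. Report the ratio of risk ratios per 10 years with its 95% CI and the interaction p-value. It should be labelled as a ratio of risk ratios, because a risk ratio per 10 years would read as the main effect of age. Keep the two age groups as descriptive rows in the forest plot, so that a departure from linearity can be seen; the sample-median cut is acceptable in that role.

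The cost is a change of SAP wording and of one model term. The age model has the same number of parameters as the gender example in Section 8.8, and no new data are needed. The test will assume an approximately log-linear gradient, and the modified Poisson fallback in Section 8.4 may be needed more often.

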8.9. Exploratory Analysis

Proportions of those patients achieving the binary outcomes described in Section 5.5 will be described by frequencies and percentages by trial arm and for the overall population and by prespecified subgroups. No statistical significance testing will be performed for these analyses.

Mean (SD) and median (IQR) percentage change from baseline will be tabulated for each lipid measure.

The DSS Evaluation Questionnaire consists of 11 questions (see Table 43). Questions 1 to 10 are Likert responses scored from 1 (strongly disagree) to 5 (strongly agree) adapted from a previously published system usability scale (SUS).¹⁸ Question 11 is an additional question to capture overall user-friendliness of the DSS tool scored from six options from 'worst imaginable' to 'best imaginable'. Responses to the DSS Evaluation Questionnaire by the clinicians at DSS sites will be summarised descriptively using:

- mean (and range) score for each question (negative items (in italics in Table 43) will be reverse coded
- proportion of patients agreeing and disagreeing with each question (Questions 1 to 10)
- proportion who rated the DSS poor or worse in terms of overall user-friendliness (Question 11)
- proportion who deemed the DSS good or better in terms of overall user-friendliness (Question 11).

An overall usability score scaled from 0 to 100 will be computed from responses to Questions 1 to 10 only.¹⁸ A value of 1 is subtracted from the score of odd-numbered questions and the respondent's score is subtracted from 5 for even-numbered questions. These new values are summed and multiplied by 2.5 to give a score ranging from 0 to 100. Higher scores indicated greater usability.

Two additional open-ended questions (not included in the published SUS) have been included to capture suggestions for improvement of the DSS in terms of usability and examples of where the tool has been impactful in clinical practice. Responses to this question will be evaluated separately and are outside the scope of this SAP.

8.10. Sensitivity Analysis

Two sensitivity analyses are planned for this study as below:

- A complete case analysis of the primary outcome will be undertaken as a sensitivity analyses. This will include all eligible and randomised patients whose outcomes are

Imperial Clinical Trials Unit	ZODIAC STATISTICAL ANALYSIS PLAN – MAIN ANALYSIS	V1 17 th Jan 2024
----------------------------------	--	------------------------------

available by 16 weeks. Patients in population will be analysed according to the randomised group allocated to the cluster (site) in which they are followed, either SoC or DSS.

- Full ITT analysis including patients who died and incorporating multiple imputation.

8.11. Modelling and Simulation Based Analyses

The modelling and simulation based analyses will be conducted by Axtria. Axtria will develop their own statistical analysis plan which can be read in conjunction with this SAP.

9. Statistical Considerations

9.1. Missing Baseline Data

Every effort will be taken to minimise missing data. If baseline values are missing, to avoid a loss of power within the analyses which adjust for baseline values, these values will be imputed with the mean baseline value calculated from the non-missing values using pooled data from both treatment groups.

9.2. Multiple Comparisons

No multiplicity adjustments will be performed for the analysis of secondary outcomes, and results will be viewed as hypothesis-generating.

10. Software

All analyses will be conducted in Stata version 17, with the exception of the multi level multiple imputation that will be conducted in R version 4.2.1 or higher.

11. Appendix A: Primary Outcome Algorithm

Study%20Specific%20
Procedure%20Manu

12. Appendix B: Tables to Present

12.1. Recruitment

Table 7: Randomisation stratification variables

		Number of Sites		
		DSS	Control	Overall
Sites, N (%)	United Kingdom			
	Italy			
	Spain			
	Total			
Clinic Type, N (%)	Secondary care			
	Tertiary care			
	Mix of both			
	Total			

Table 8: Number of patients per site per country

		Total N
Total Patients		
Centre	Name of site	N (%)
United Kingdom	...	
	...	
	...	
Italy	...	
	...	
	...	
Spain	...	
	...	
	...	

Imperial Clinical Trials Unit	ZODIAC STATISTICAL ANALYSIS PLAN – MAIN ANALYSIS	V1 17 th Jan 2024
-------------------------------	--	------------------------------

Table 9: Reasons for exclusion of sites

Exclusion reason (patients)	N (%)
Unable to capture/ provide data on patients with ACS during admission and follow up	
Unable or unwilling to use lipid lowering treatments other than statins for ACS care	
Unable or unwilling to access and undertake training for the DSS	
Inadequate internet connection at site and the ability to access the DSS	
Site did not proceed	

Table 10: Reasons for exclusion of participants from enrolled sites

Exclusion reason (patients)	N (%)
Aged <18 to ≥ 80 years old	
Unable to provide written informed consent	
Patient rescinded consent (changed mind before any data collected)	
LDL-C measurement < 1.8 mmol/L at admission	
Unstable angina	
ACS event not verified in time	
>72 hours after ACS event	

12.2. Baseline Characteristics

Table 11: Baseline demographics of randomised patients at screening

		DSS	Control	Overall
Age (years)				
	N (Missing)			
	Mean, SD			
	Median, IQR			
	Min, Max			
Sex (assigned at birth), n (%)				
	N (Missing)			
	Female			
	Male			
Ethnicity, n (%)				
	N (Missing)			
	White			
	Black			
	Asian			
	Mixed Race			
	North African			
	Other			

Imperial Clinical Trials Unit	ZODIAC STATISTICAL ANALYSIS PLAN – MAIN ANALYSIS	V1 17 th Jan 2024
-------------------------------	--	------------------------------

Table 12: Type of index event experienced by randomised patients

	DSS	Control	Overall
Index Acute Coronary Syndrome (ACS) Event, n (%)			
N (Missing)			
STEMI			
NSTEMI			

Table 13: Cardiovascular risk factor history of randomised patients PRIOR to index event admission

	DSS	Control	Overall
Diabetes Mellitus Diagnosis, n (%)			
N (Missing)			
Yes			
No			
If yes*			
Prediabetes			
Type-1			
Type-2			
Gestational			
Coronary Artery Disease Diagnosis, n (%)			
N (Missing)			
Yes			
No			
If yes*			
Myocardial Infarction			
Coronary Artery Bypass Surgery			
Angioplasty/PCI			
Cerebrovascular Disease Diagnosis, n (%)			
N (Missing)			
Yes			
No			
If yes*			
Stroke/TIA			
Carotid artery stenosis			
Aneurysms			
Peripheral Artery Disease Diagnosis, n (%)			
N (Missing)			
Yes			
No			
If yes*			
Arteriosclerosis Obliterans			
Arterial Insufficiency of the Legs			
Claudication			
Abdominal Aortic Aneurysm Diagnosis, n (%)			
N (Missing)			
Yes			
No			
Time since first ASCVD Diagnosis (years)			

Imperial Clinical Trials Unit	ZODIAC STATISTICAL ANALYSIS PLAN – MAIN ANALYSIS	V1 17 th Jan 2024
-------------------------------	--	------------------------------

	N (Missing)			
	Mean, SD			
	Median, IQR			
	Min, Max			
Smoking status	N (Missing)			
	Current regular			
	Current occasional			
	Former regular			
	Never			

*patient may answer yes to one of more of the specific categories

Table 14: Baseline laboratory measurements and observations of randomised patients

		DSS	Control	Overall
eGFR (mL/min/1.73m²)				
	N (Missing)			
	Mean, SD			
	Median, IQR			
	Min, Max			
hs-CRP (mg/dL)				
	N (Missing)			
	Mean, SD			
	Median, IQR			
	Min, Max			
Systolic blood pressure (mmHg)				
	N (Missing)			
	Mean, SD			
	Median, IQR			
	Min, Max			

Imperial Clinical Trials Unit	ZODIAC STATISTICAL ANALYSIS PLAN – MAIN ANALYSIS	V1 17 th Jan 2024
-------------------------------	--	------------------------------

Table 15: Concomitant medications of randomised patients at screening

		DSS	Control	Overall
Antiplatelet medication				
	N (Missing)			
	Yes			
	No			
If yes*	Aspirin			
	Clopidogrel			
	Prasugel			
	Ticagrelor			
	Other			
Anticoagulant medication				
	N (Missing)			
	Yes			
	No			
Blood pressure medication				
	N (Missing)			
	Yes			
	No			
If yes*	Angiotensin-II receptor blocker			
	ACE inhibitor			
	Calcium channel blocker			
	Beta-blocker			
	Aspirin			
Diabetes related medication				
	N (Missing)			
	Yes			
	No			
If yes*	Insulin			
	Sulfonylurea			
	SGLT2 inhibitor			
Taking any aspirin (if not specified as antiplatelet)				
	N (Missing)			
	Yes			
	No			

Imperial Clinical Trials Unit	ZODIAC STATISTICAL ANALYSIS PLAN – MAIN ANALYSIS	V1 17 th Jan 2024
-------------------------------	--	------------------------------

Table 16: Lipid lowering therapy prior to admission

n (%)		DSS	Control	Overall
Prior to admission in the last month, was patient was taking any cholesterol lowering medication?				
	N (Missing)			
	No			
	Yes, monotherapy			
	Yes, combination therapy			
	Two drugs			
	≥Three drugs			
If yes, what class*	Statin			
	Ezetimibe			
	Bempedoic Acid			
	Bile sequestrants			
	PCSK9 Monoclonals			
	PCK9 siRNA			
	Other			
Patient compliant with LLT	Yes			
	No			
	Missing			
LLT intensity (expected LDL reduction), n(%)				
Monotherapy:				
	Low (<30%)			
	Moderate (≥30% to <50%)			
	High (≥50% to <65%)			
	Very high potency (≥65%)			
	Potency undefined			
Combination:				
	Low (<30%)			
	Moderate (≥30% to <50%)			
	High (≥50% to <65%)			
	Very high potency (≥65%)			
	Potency undefined			

Table 17: Lipid lowering therapy at discharge

n (%)		DSS	Control	Overall
At discharge, was patient was taking any cholesterol lowering medication?				
	N (Missing)			
	No			
	Yes, monotherapy			
	Yes, combination therapy			
	Two drugs			
	≥ Three drugs			
If yes, what class*	Statin			
	Ezetimibe			
	Bempedoic Acid			

Imperial Clinical Trials Unit	ZODIAC STATISTICAL ANALYSIS PLAN – MAIN ANALYSIS	V1 17 th Jan 2024
-------------------------------	--	------------------------------

	Bile sequestrants			
	PCSK9 Monoclonals			
	PCK9 siRNA			
	Other			
LLT potency				
Monotherapy:				
	Low (<30%)			
	Moderate (≥30% to <50%)			
	High (≥50% to <65%)			
	Very high potency (≥65%)			
	Potency undefined			
Combination:				
	Low (<30%)			
	Moderate (≥30% to <50%)			
	High (≥50% to <65%)			
	Very high potency (≥65%)			
	Potency undefined			

Table 18: Lipid profile at baseline (closest measure prior to or during admission): all patients

Measure		DSS	Control	Overall
LDL-C (mmol/L)				
	N (Missing)			
	Mean, SD			
	Median, IQR			
	Min, Max			
Non HDL-C (mmol/L)				
	N (Missing)			
	Mean, SD			
	Median, IQR			
	Min, Max			
HDL-C (mmol/L)				
	N (Missing)			
	Mean, SD			
	Median, IQR			
	Min, Max			
Total Cholesterol (mmol/L)				
	N (Missing)			
	Mean, SD			
	Median, IQR			
	Min, Max			
Triglycerides (mmol/L)				
	N (Missing)			
	Mean, SD			

Imperial Clinical Trials Unit	ZODIAC STATISTICAL ANALYSIS PLAN – MAIN ANALYSIS	V1 17 th Jan 2024
-------------------------------	--	------------------------------

	Median, IQR			
	Min, Max			

Table 19: Lipid profile at baseline (closest measure prior to or during admission): LLT naïve patients

Measure		DSS	Control	Overall
LDL-C (mmol/L)				
	N (Missing)			
	Mean, SD			
	Median, IQR			
	Min, Max			
Non HDL-C (mmol/L)				
	N (Missing)			
	Mean, SD			
	Median, IQR			
	Min, Max			
HDL-C (mmol/L)				
	N (Missing)			
	Mean, SD			
	Median, IQR			
	Min, Max			
Total Cholesterol (mmol/L)				
	N (Missing)			
	Mean, SD			
	Median, IQR			
	Min, Max			
Triglycerides (mmol/L)				
	N (Missing)			
	Mean, SD			
	Median, IQR			
	Min, Max			

Table 20: Lipid profile at baseline (closest measure prior to or during admission): non-LLT naïve patients

Measure		DSS	Control	Overall
LDL-C (mmol/L)				
	N (Missing)			
	Mean, SD			
	Median, IQR			
	Min, Max			
Non HDL-C (mmol/L)				
	N (Missing)			

	Mean, SD			
	Median, IQR			
	Min, Max			
HDL-C (mmol/L)				
	N (Missing)			
	Mean, SD			
	Median, IQR			
	Min, Max			
Total Cholesterol (mmol/L)				
	N (Missing)			
	Mean, SD			
	Median, IQR			
	Min, Max			
Triglycerides (mmol/L)				
	N (Missing)			
	Mean, SD			
	Median, IQR			
	Min, Max			

12.3.Study withdrawals

Table 21: Study completion and reason for non-completion

Completion status	No. of patients (%)		
	DSS	Control	Overall
Completed Study			
Completed study with outcome data at 16 weeks			
Did Not Complete Study			
Patient withdrew consent			
Death			
Lost to follow-up			
No longer meets eligibility criteria			
Adverse event			
Investigator decision			
Other			
.....			

Imperial Clinical Trials Unit	ZODIAC STATISTICAL ANALYSIS PLAN – MAIN ANALYSIS	V1 17 th Jan 2024
-------------------------------	--	------------------------------

Table 22: Timing of study withdrawals

Time of withdrawal On or before:	No. of patients (%)		
	DSS	Control	Overall
Week 4			
Week 8			
Week 12			
Week 16			
Total			

